10.6. Study Management Structure

10.6.1. Trial Steering Committee

The Trial Steering Committee (TSC) convened for the safety run-in part of the study, will continue their role in the phase IIa part of the study. The TSC includes: an independent Chair; two independent clinicians; a patient representative; the Chief Investigator and Trial Coordinator. The role of the TSC will be to provide overall supervision of the trial including monitoring progress, adherence to the protocol and patient safety. It will also consider new information relevant to the

research question as it becomes available and as necessary, advise the TMG on operational issues.

Where possible, membership will also include a lay/consumer representative

10.6.2. Trial Management Group

The Trial Management Group (TMG) convened for the safety run-in part of the study, will continue their role in the phase IIa part of the study. The TMG includes: the Chief Investigator, co-investigators and identified key collaborators, the trial statistician and trial co-ordinator. Principle Investigators and key study personnel may be invited to join the TMG as appropriate to ensure representation from a range of sites and professional groups.

Notwithstanding the legal obligations of the Sponsor and Chief Investigator, the TMG will have operational responsibility for the day to day conduct of the trial.

10.6.3. Safety Review Committee (Safety run-in only)

The Safety Review Committee (SRC) will consist of the Chief Investigator, the Trial Coordinator and local investigators or delegates from each actively recruiting site. An AstraZeneca Medical Science Director and a Medical Advisor from Cancer Research UK's Drug Development Office will also be invited to attend. The ICTU-Ca Senior Trials Manager and Study Statistician may attend as appropriate. The committee will evaluate safety data acquired during the safety run-in part of the study only, and make recommendations on dose de-escalation / modification decisions in the safety run-in phase and confirm the dose to take forward to the phase IIa part of the study.

10.6.4. Independent Data Monitoring Committee (Phase IIa only)

An Independent Data Monitoring Committee (IDMC) will be convened to monitor data collected during the phase IIa part of the study only, and make recommendations to the TSC on whether there are any ethical or safety reasons as to why the trial should not continue. It will consist of an independent Chair, an independent statistician and an independent clinician.

10.7. Monitoring

The study will be monitored periodically by monitors in the UK to assess the progress of the study, verify adherence to the protocol, ICH GCP E6 guidelines and other national/international requirements and to review the completeness, accuracy and consistency of the data.

Monitoring procedures and requirements will be documented in a Monitoring Plan. Monitoring will be proportionate to the objective, purpose, design, size, complexity, blinding, endpoints and risks associated with the clinical trial. The appropriate level and nature of monitoring required for the clinical trial will be assessed by undertaking a formal risk assessment analysis of the study.

10.8. Quality Control and Quality Assurance

Quality Control will be performed according to ICTU internal procedures. The study may be audited by a Quality Assurance representative of the Sponsor. All necessary data and documents will be made available for inspection.

10.9. Disclosure of Data and Publication

Information concerning the study, patent applications, processes, scientific data or other pertinent information is confidential and remains the property of the Sponsor. The investigator may use this information for the purposes of the study only.

It is understood by the investigator that the Sponsor will use information developed in this clinical study in connection with the development of the IMP and, therefore, may disclose it as required to other clinical investigators and to Regulatory Authorities. In order to allow the use of the information derived from this clinical study, the investigator understands that he/she has an obligation to provide complete test results and all data developed during this study to the Sponsor.

Verbal or written discussion of results prior to study completion and full reporting, should only be undertaken with written consent from the Sponsor.

Therefore all information obtained as a result of the study will be regarded as CONFIDENTIAL, at least until appropriate analysis and review by the investigator(s) is completed.

Investigators may only present data separately to the total data available, with the permission of the TMG, and not less than 6 months after the publication of the main results.

AstraZeneca has the right to review all abstracts, papers or other research communications prior to their submission to journals, meetings or conferences.

13. APPENDICES

Appendix A: Guidelines for Evaluation of Objective Tumour Response Using RECIST 1.1 (Response Evaluation Criteria in Solid Tumours)

(ICTU-Cancer guidance document v2.0 dated 17 November 2014)

Response and progression will be evaluated in this study using the new international criteria proposed by the revised Response Evaluation Criteria in Solid Tumours (RECIST) guideline (version 1.1) [*Eur J Ca* 45:228-247, 2009]. Changes in the largest diameter (unidimensional measurement) of the tumour lesions and the shortest diameter in the case of malignant lymph nodes are used in the RECIST criteria.

Definition of Disease Parameters

Measurable disease Must be accurately measured in a least one dimension (longest diameter in the plane of measurement is to be recorded) with a minimum size of:

- 10mm by CT scan (CT scan slice thickness no greater than 5mm; when CT scans have slice thickness >5mm, the minimum size should be twice the slice thickness).
- 10mm caliper measurement by clinical exam (lesions which cannot be accurately measured with calipers should be recorded as non-measurable).
- 20mm by chest X-ray.

Note: Tumour lesions situated in a previously irradiated area or in an area subjected to other loco-regional therapy are usually not considered measurable unless there has been demonstrated progression in the lesion. Study protocols should detail the conditions under which such lesions would be considered measurable.

Malignant lymph nodes Criteria for lymph nodes given as ≥ 15 mm short axis for target lesions and 10mm to <15mm for non-target lesions. Nodes under 10mm to be considered non-pathological.

Non-measurable disease All other lesions, including small lesions (longest diameter <10 mm or pathological lymph nodes with 10 to <15 mm short axis), as well as truly non-measurable lesions. Lesions considered truly non-measurable include; leptomeningeal disease, ascites, pleural/pericardial effusions, inflammatory breast disease, lymphangitic involvement of skin or lung, abdominal masses/abdominal organomegaly identified by physical exam that is not measurable by reproducible imaging techniques.

Note: Lytic bone lesions or mixed lytic-blastic lesions with identifiable soft tissue components that can be evaluated by cross-sectional imaging techniques such as CT or MRI can be considered measurable if the soft tissue component meets the definition of measurability described above.

'Cystic lesions' thought to represent cystic metastases can be considered measurable if they meet the definition of measurability described above. However, if non-cystic lesions are present in the same patient, these are preferred for selection as target lesions.

Target lesions All measurable lesions up to a maximum of 2 lesions per organ and 5 lesions in total, representative of all involved organs, should be identified as target lesions and recorded and measured at baseline. Target lesions should be selected on the basis of their size (lesions with the longest diameter) and be representative of all involved organs, as well as their suitability for reproducible repeated measurements. All measurements should be recorded in metric notation

using calipers if clinically assessed. A sum of the diameters (longest for non-nodal lesions, short axis for nodal lesions) for all target lesions will be calculated and reported as the baseline sum diameters, which will be used as reference to further characterize any objective tumour regression in the measurable dimension of the disease. If lymph nodes are to be included in the sum, only the short axis will contribute.

Non-target lesions All lesions (or sites of disease) not identified as target lesions, including pathological lymph nodes and all non-measurable lesions, should be identified as non-target lesions and be recorded at baseline. Measurements of these lesions are not required and they should be followed as 'present', 'absent' or in rare cases, 'unequivocal progression'.

Methods of Measurement

All measurements should be taken and recorded in metric notation using a ruler or calipers. All baseline evaluations should be performed as closely as possible to the beginning of treatment and never more than 4 weeks before the beginning of the treatment.

The same method of assessment and the same technique should be used to characterize each identified and reported lesion at baseline and during follow-up.

CT/MRI: CT is the best currently available and reproducible method to measure lesions selected for response assessment. MRI is also acceptable in certain situations (e.g. for body scans but not for lung).

Chest x-ray Lesions on chest x-ray may be considered measurable lesions if they are clearly defined and surrounded by aerated lung. However, CT is preferable.

Clinical lesions Clinical lesions will only be considered measurable when they are superficial and ≥ 10 mm in diameter as assessed using calipers. For the case of skin lesions, documentation by colour photography, including a ruler to estimate the size of the lesion, is recommended.

Ultrasound (US) should not be used to measure tumour lesions.

Tumour markers Tumour markers alone cannot be used to assess response. If markers are initially above the upper normal limit, they must normalize for a patient to be considered in complete clinical response. Specific guidelines for both CA-125 response (in recurrent ovarian cancer) and PSA response (in recurrent prostate cancer) have been published [*JNCI* 96:487-488, 2004; *J Clin Oncol* 17, 3461-3467, 1999; *J Clin Oncol* 26:1148-1159, 2008]. In addition, the Gynecologic Cancer Intergroup has developed CA-125 progression criteria which are to be integrated with objective tumour assessment for use in first-line trials in ovarian cancer [*JNCI* 92:1534-1535, 2000].

Cytology, Histology Can be used in rare cases (e.g. for evaluation of residual masses to differentiate between Partial Response and Complete Response or evaluation of new or enlarging effusions to differentiate between Progressive Disease and Response/Stable Disease).

Endoscopy, Laparoscopy Use of endoscopy and laparoscopy is not advised. However, they can be used to confirm complete pathological response.

New Lesions

It is sometimes reasonable to incorporate the use of FDG-PET scanning to complement CT in assessment of progression (particularly possible 'new' disease). New lesions on the basis of FDG-PET imaging can be identified according to the following algorithm:

Negative FDG-PET at baseline, with a positive FDG-PET at follow-up is PD based on a new lesion.

No FDG-PET at baseline and a positive FDG-PET at follow up:

- If the positive FDG-PET at follow-up corresponds to a new site of disease confirmed by CT, this is PD.
- If the positive FDG-PET at follow-up is not confirmed as a new site of disease on CT, additional follow-up CT scans are needed to determine if there is truly progression occurring at that site (if so, the date of PD will be the date of the initial abnormal FDG-PET scan).
- If the positive FDG-PET at follow-up corresponds to a pre-existing site of disease on CT that is not progressing on the basis of the anatomic images, this is no PD.

Response Criteria

Evaluation of Target Lesions

Complete Response (CR): Disappearance of all target lesions. Any pathological lymph nodes (whether target or non-target) must have reduction in short axis to <10 mm.

Partial Response (PR): At least a 30% decrease in the sum of the diameters of target lesions, taking as reference the baseline sum diameters

Progressive Disease (PD): At least a 20% increase in the sum of the diameters of target lesions, taking as reference the smallest sum on study (this may include the baseline sum). The sum must also demonstrate an absolute increase of at least 5mm.

Stable Disease (SD): Neither sufficient shrinkage to qualify for PR nor sufficient increase to qualify for PD.

Evaluation of Non-Target Lesions

Complete Response (CR): Disappearance of all non-target lesions and normalization of tumour marker levels. All lymph nodes must be non-pathological in size (<10 mm short axis)

Non-CR/Non-PD: Persistence of one or more non-target lesion(s) and/or maintenance of tumour marker level above the normal limits

Progressive Disease (PD): Unequivocal progression of existing non-target lesions.

- When patient has measurable disease – to achieve 'unequivocal progression' on the basis of the non-target disease, there must be an overall level of substantial worsening in non-
Confidential

target disease such that, even in presence of SD or PR in target disease, the overall tumour burden has increased sufficiently to merit discontinuation of therapy. A modest 'increase' in the size of one or more non-target lesions is usually not sufficient to qualify for unequivocal progression status.

- When patient has none-measurable disease – there is no measurable disease assessment to factor into the interpretation of an increase in non-measurable disease burden. Because worsening in non-target disease cannot be easily quantified, a useful test that can be applied is to consider if the increase in overall disease burden based on change in non-measurable disease is comparable in magnitude to the increase that would be required to declare PD for measurable disease. Examples include an increase in a pleural effusion from 'trace' to 'large' or an increase in lymphangitic disease from localised to widespread.

Evaluation of Best Overall Response

Summary of overall response status calculation at each time point, for patients who have measurable disease at baseline.

Target Lesions	Non-Target Lesions	New Lesions	Overall Response	Best Overall Response when Confirmation is Required*
CR	CR	No	CR	≥4 wks. Confirmation**
CR	Non-CR/Non-PD	No	PR	≥4 wks. Confirmation**
CR	Not evaluated	No	PR	
PR	Non-CR/Non-PD/not evaluated	No	PR	
SD	Non-CR/Non-PD/not evaluated	No	SD	documented at least once ≥4 wks. from baseline**
Not all evaluated	Non-PD	No	Not evaluated	
PD	Any	Yes or No	PD	no prior SD, PR or CR
Any	PD***	Yes or No	PD	
Any	Any	Yes	PD	

* See RECIST 1.1 manuscript for further details on what is evidence of a new lesion.

** Only for non-randomized trials with response as primary endpoint.

*** In exceptional circumstances, unequivocal progression in non-target lesions may be accepted as disease progression.

Note: Patients with a global deterioration of health status requiring discontinuation of treatment without objective evidence of disease progression at that time should be reported as "symptomatic deterioration." Every effort should be made to document the objective progression even after discontinuation of treatment.

For Patients with Non-Measurable Disease (i.e., Non-Target Disease)

Non-Target Lesions	New Lesions	Overall Response
CR	No	CR
Non-CR/non-PD	No	Non-CR/non-PD*
Not all evaluated	No	not evaluated
Unequivocal PD	Yes or No	PD
Any	Yes	PD

* 'Non-CR/non-PD' is preferred over 'stable disease' for non-target disease since SD is increasingly used as an endpoint for assessment of efficacy in some trials so to assign this category when no lesions can be measured is not advised

Duration of Response

Duration of overall response: The duration of overall response is measured from the time measurement criteria are met for CR/PR (whichever status is recorded first) until the first date that recurrence or PD is objectively documented, (taking as reference for PD the smallest measurements recorded on study).

Duration of stable disease: SD is measured from the start of the treatment (in randomised trials, from the date of randomization) until the criteria for disease progression are met, taking as reference the smallest sum on study (if baseline sum is the smallest, this is the reference for calculation of PD). The clinical relevance of the duration of SD varies for different studies and diseases. This time interval should take into account the expected clinical benefit that such a status may bring to the population under study. If the proportion of patients achieving stable disease for a minimum period of time is an endpoint of importance in a particular trial, the protocol should specify the minimal time interval required between two measurements for determination of stable disease.

Response Review

For trials where the objective response (CR and PR) is the primary endpoint it is recommended that all responses be reviewed by an expert(s) independent of the study. Simultaneous review of the patients' files and radiological images is the best approach.

Appendix B:**Guidance on Potential Interactions with Concomitant Medications (dated 9th July 2010)***

*The appendix should not be taken as a definitive list. All conmeds should be checked locally for Drug Drug Interactions by checking the Summary of Product Characteristics for each drug. This information is publically available online (<http://www.medicines.org.uk>).

1. Drugs affecting CYP3A4 or CYP2D6 metabolism that AstraZeneca strongly recommend are not combined with AZD4547**Table 1: Potent CYP3A4 or CYP2D6 inhibitors may increase exposure to AZD4547 more than 5-fold**

Fluoxetine	Minimum of 35 days washout prior to AZD4547 administration and for 14 days following discontinuation of AZD4547
Ketoconazole Ritonavir Saquinavir Indanavir Nefazodone Nelfinavir Paroxetine Quinidine	Minimum of 2 weeks washout prior to AZD4547 administration and for 2 weeks following discontinuation of AZD4547
Itraconazole Clarithromycin (250mg or 500mg bd)	Minimum of 1 week washout prior to AZD4547 administration and for 2 weeks following discontinuation of AZD4547

Table 2: Potent Inducers of CYP3A4 may reduce exposure to AZD4547 by more than 3-fold

Barbiturates Carbamazepine Phenytoin Rifampicin, Rifabutin Troglitazone	Minimum of 2 weeks washout prior to AZD4547 administration and for 2 weeks following discontinuation of AZD4547
St John's Wort	Minimum of 3 weeks washout prior to AZD4547 administration and for 2 weeks following discontinuation of AZD4547

There are currently no data confirming that there is a pharmacokinetic (PK) interaction between these agents and AZD4547; a potential interaction is considered on the basis of preclinical data only. This list is not intended to be exhaustive, and a similar restriction will apply to other agents that are known to strongly modulate CYP3A4 or CYP2D6 activity. Appropriate medical judgment is required. Please contact the study coordinator at ICTU-Cancer with any queries you have on this issue.

2. Drugs affecting CYP3A4 metabolism that AstraZeneca considers may be allowed with caution

Table 3: Moderate Inhibitors of CYP3A4 or CYP2D6 may increase exposure to AZD4547

Warning of possible interaction	
Aprepitant Diltiazem Duloxetine Erythromycin Fluconazole Sertraline Terbinafine Verapamil	Drugs are permitted but caution should be exercised and patients monitored closely for possible drug interactions. Please refer to full prescribing information for all drugs prior to co-administration with AZD4547.
Grapefruit juice Seville oranges (and other products containing Seville oranges)	Patients should abstain from eating large amounts of grapefruit and Seville oranges (and other products containing these fruits e.g., grapefruit juice or marmalade) during the study (i.e. no more than a small glass of grapefruit juice (120 mL) or half a grapefruit or 1-2 teaspoons (15 g) of Seville orange marmalade daily).

3. Medicines that are significantly metabolised by CYP3A4 that AstraZeneca strongly recommend are not combined with AZD4547

Table 4: Exposure, pharmacological action and toxicity may be increased by inhibition of CYP3A4 by AZD4547

Alfentanil Cyclosporin Tacrolimus Atorvastatin Lovastatin Simvastatin	Minimum of 1 week washout prior to AZD4547 administration and for 2 weeks following discontinuation of AZD4547
Carbamazepine	Minimum of 2 weeks washout prior to AZD4547 administration and for 2 weeks following discontinuation of AZD4547.

There are currently no data confirming that there is a pharmacokinetic (PK) interaction between these agents and AZD4547; a potential interaction is considered on the basis of preclinical data only. This list is not intended to be exhaustive, and a similar restriction will apply to other agents with narrow therapeutic windows that are known to depend on CYP3A4 for metabolism. Appropriate medical judgment is required. Please contact AstraZeneca with any queries you have on this issue.

4. MEDICINES THAT ARE SIGNIFICANTLY METABOLISED BY CYP3A4 THAT STRAZENECA CONSIDERS MAY BE ALLOWED WITH CAUTION

Table 5: Exposure, pharmacological action and toxicity may be increased by inhibition of CYP3A4 by AZD4547

Warning of possible interaction:	
Alprazolam Erythromycin Felodipine Isradipine Midazolam Nifedipine Tamoxifen Trazodone Triazolam And possibly other calcium antagonists Methylprednisolone Pimozide Quinidine	Drugs are permitted but caution should be exercised and patients monitored closely for possible drug interactions. Please refer to full prescribing information for all drugs prior to co-administration with AZD4547.

5. Drugs that may prolong QT interval

The drugs listed in this section are taken from information provided by The Arizona Center for Education and Research on Therapeutics and The Critical Path Institute, Tucson, Arizona and Rockville, Maryland.

Ref: <http://www.arizonacert.org/medical-pros/drug-lists/drug-lists.htm>

5.1 Drugs known to prolong QT interval

The following drugs are known to prolong QT interval or induce Torsades de Pointes and should not be combined with AZD4547. Recommended washout periods following cessation of treatment with these agents are provided in the following table.

Contraindicated drug	Washout period prior to AZD4547 start
Droperidol	2 days
Erythromycin	
Procainamide	
Cisapride	7days
Clarithromycin	
Disopyramide	
Dofetilide	
Domperidone*	

Contraindicated drug	Washout period prior to AZD4547 start
Ibutilide	
Quinidine	
Sotalol	
Sparfloxacin	
Thioridazine	
Bepriidil	14 days
Chlorpromazine	
Halofantrine	
Haloperidol	
Mesoridazine	
Levomethadyl	4 weeks
Methadone	
Pimozide	
Arsenic trioxide	6 weeks*
Pentamidine	8 weeks
Amiodarone	1 year
Chloroquine	

* Estimated value as pharmacokinetics of arsenic trioxide has not been studied

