7. Refractory nausea and vomiting, chronic gastrointestinal diseases, inability to swallow the formulated IMP or previous significant bowel resection that would preclude absorption of AZD4547 or anastrozole or letrozole
8. History of hypersensitivity to anastrozole or letrozole
9. History of another malignancy within 5 yrs prior to starting study treatment, except adequately treated basal or squamous cell carcinoma of the skin, carcinoma of the cervix and the disease under study

10. Any of the following ophthalmological criteria:*

- Current evidence or previous history of retinal pigmented epithelium detachment (RPED)
- Previous laser treatment or intra-ocular injection for treatment of macular degeneration
- Current evidence or previous history of soft drusen, drusenoid RPE detachment and wet macular degeneration.
- Current evidence or previous history of retinal vein occlusion (RVO)
- Current evidence or previous history of retinal degenerative diseases (e.g. hereditary)

*Patients with uncontrolled glaucoma or intra-ocular pressure >21 mmHg at screening should be referred for ophthalmological management and the condition controlled prior to first dose of study treatment.

11. Concurrent treatment with another investigational agent or use of another investigational agent within 30 days or 5 half lives, whichever is longer, preceding the first dose of study treatment
12. Concurrent treatment with prohibited medications and wash out period for that drug will not have been completed before starting study medication (see Appendix B)

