6.2.11. Drug Interactions/Precautions

6.2.11.1. Restrictions

The following restrictions apply while the patient is receiving study treatment and for the specified times before and after:

1. All patients should avoid concomitant use of drugs, herbal supplements and/or ingestion of foods known to modulate CYP3A4 or CYP2D6 enzyme activity and drugs that are known to be CYP3A4 substrates from the time they enter the screening period until 2 weeks after the last dose of study treatment. Please refer to Appendix B for further details.
2. Patients must not use oestrogen-containing agents such as hormone replacement therapy.
3. Patients with uncontrolled glaucoma or intra-ocular pressure ≥ 21 mm Hg at screening should be referred for ophthalmological management and the condition controlled prior to first dose.

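### Appendix B contraindicates erythromycin, quinidine and pimozide on QT grounds in 5.1 but marks them as permitted with caution in Table 5 (and erythromycin in Table 3), with no general rule on which list prevails

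*Protocol*

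**What the plan says.** Appendix B of the protocol holds several drug lists built on two different grounds. Tables 1 to 5 concern CYP3A4 and CYP2D6 interactions; section 5 concerns QT prolongation.

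- **Section 5.1:** "The following drugs are known to prolong QT interval or induce Torsades de Pointes and should not be combined with AZD4547". Its table of contraindicated drugs includes erythromycin, quinidine and pimozide, with washouts.
- **Table 5:** the drugs are "Alprazolam Erythromycin Felodipine Isradipine Midazolam Nifedipine Tamoxifen Trazodone Triazolam And possibly other calcium antagonists Methylprednisolone Pimozide Quinidine", and their status is "Drugs are permitted but caution should be exercised and patients monitored closely for possible drug interactions".
- **Table 3:** the same permission is given to "Aprepitant Diltiazem Duloxetine Erythromycin Fluconazole Sertraline Terbinafine Verapamil".
- **Table 1:** potent inhibitors that should not be combined with AZD4547. The group with a minimum 2-week washout is "Ketoconazole Ritonavir Saquinavir Indanavir Nefazodone Nelfinavir Paroxetine Quinidine".

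In the main text, 6.2.11.1 tells patients to avoid drugs and foods that modulate CYP3A4 or CYP2D6. The same rule covers "drugs that are known to be CYP3A4 substrates from the time they enter the screening period until 2 weeks after the last dose". The section then adds: "Please refer to Appendix B for further details". Exclusion 12 and section 5.2.11 also rely on Appendix B to identify prohibited medication and its washout.

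**The concern.** One appendix gives opposite instructions for the same three drugs. A site that looks up erythromycin in Table 3 or Table 5 finds it permitted; a site that looks it up in 5.1 finds it contraindicated because of QT prolongation or Torsades de Pointes. The protocol itself treats QT as a hazard: a resting QTc above 470 ms excludes a patient, and a QTc above 500 ms or a rise of more than 60 ms counts as a dose-limiting toxicity, a definition carried over to severe toxicity in phase IIa. Table 5 is also the list of drugs whose exposure AZD4547 may raise. What is at stake is patient safety and protocol compliance during treatment, not any statistical quantity.

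**Working it through.** No arithmetic beyond counting applies. The check is a cross-match of named drugs.

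**List sizes** (named drugs only): Table 1 has 11, Table 3 has 8, Table 5 has 12, and section 5.1 has 25.

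**Overlaps of 5.1 with the permissive tables:** with Table 5, erythromycin, quinidine and pimozide (3); with Table 3, erythromycin (1). That is 3 drugs out of 25, in 3 + 1 = 4 entries.

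| Drug | 5.1 (QT) | Table 1 | Table 3 | Table 5 |
|---|---|---|---|---|
| Erythromycin | contraindicated, 2 days | not listed | permitted with caution | permitted with caution |
| Quinidine | contraindicated, 7 days | barred, at least 2 weeks | not listed | permitted with caution |
| Pimozide | contraindicated, 4 weeks | not listed | not listed | permitted with caution |

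The 5.1 washouts are read from the first row of each group, since the cells appear merged; drugs run alphabetically within each group, which supports the reading. The conflict between contraindicated and permitted does not depend on it.

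**Is there a precedence rule?** The only wording of that kind is in 5.2, which permits its own drugs notwithstanding other exclusions. It does not cover Table 3, Table 5 or 5.1.

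**What the main text adds at entry.** Exclusion 5c bars medication known to prolong QT. Exclusion 1d bars CYP3A4 substrates, and potent CYP3A4 or CYP2D6 inhibitors, within 2 weeks before first dose. Table 5 classes all three drugs as CYP3A4 substrates, and Table 1 classes quinidine as a potent inhibitor. The longest applicable washouts are therefore 2 weeks for erythromycin (1d), 2 weeks for quinidine (1d and Table 1) and 4 weeks for pimozide (5.1).

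**What the main text adds on study.** Section 1.6.4 contraindicates medicines significantly metabolised by CYP3A4 during the study, and that is how Table 5 describes its own drugs. Section 6.2.11.1 restricts substrates and modulators. Section 6.2.11.2 excepts CYP3A4 substrates and potent inhibitors or inducers from the regular medication to be maintained, although it also leaves supportive medication to the investigator's discretion. All of these rules rest on CYP metabolism. Section 5.1 is the only on-study prohibition made on QT grounds.

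**Related entries in 5.2.** Five drugs conditionally permitted there are barred elsewhere in the appendix: ketoconazole, itraconazole, paroxetine and fluoxetine (Table 1) and tacrolimus (Table 4).

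**The case against.** The strongest reply is that the main text already settles the matter. Sections 1.6.4, 6.2.11.1 and 6.2.11.2 and exclusions 1d and 5c all point towards prohibition of these three drugs. Appendix B calls itself guidance, says that it is not a definitive list, asks sites to check every concomitant drug locally, and attaches a reference to full prescribing information to the permissions in Tables 3 and 5. The CYP and QT lists address different mechanisms, so a sensible reader would require a drug to clear both.

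Most of this stands, and it narrows the risk. It does not remove the explicit permissions. Section 6.2.11.1 gives the restriction and then sends the reader to Appendix B for details, where Tables 3 and 5 read as the detailed exceptions. No sentence says that a drug must clear both parts. The entry criteria do not govern a drug started later.

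A reader might also infer that quinidine could be given with no washout because Table 5 permits it. The documents do not support that: Table 5 is silent on washout, Table 1 sets a minimum of 2 weeks, and exclusion 1d requires 2 weeks at entry in any case. The 7 days in 5.1 is a discrepancy to tidy, not a shortened washout in practice.

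**Conclusion.** The inconsistency is real: three drugs, four entries, no general order of precedence. The remaining exposure is mainly a patient already on AZD4547 who is started on one of these drugs, most plausibly erythromycin for an infection, by a site that consulted only Table 3 or 5. After cycle 2 day 1, scheduled ECGs fall once per 28-day cycle, so a short course could pass between them.

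It would be going too far to infer that the protocol as a whole allows QT-prolonging drugs; the main text leans the other way. Nothing here supports a figure for QT or exposure effects, and none is claimed. Sample size, endpoints and analysis are unaffected. The conclusion rests only on the drug names and stated status in each list. It merits correction because the change is cheap and the instruction concerns safety.

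**What to change.** Three edits to Appendix B:

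1. Delete erythromycin from Table 3 (8 drugs become 7) and erythromycin, quinidine and pimozide from Table 5 (12 become 9).
2. Add at the head of the appendix: where a drug appears in more than one list, or is restricted in the main text, the most restrictive status and the longest washout apply. For quinidine this gives 2 weeks.
3. In 5.2, replace the word notwithstanding with the words subject to, so that ketoconazole, itraconazole, paroxetine, fluoxetine and tacrolimus stay barred as in Tables 1 and 4. The sentence in edit 2 cannot do this alone, because 5.2 as worded can be read as overriding other restrictions.

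The sponsor should note one consequence. Read with 1.6.4 and 6.2.11.1, the sentence in edit 2 also withdraws the permission for the drugs left in Tables 3 and 5, because the main text already restricts CYP3A4 substrates and modulators. If those permissions are intended, 1.6.4, exclusion 1d and 6.2.11.1 need a matching exception.

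The cost is an appendix amendment (four entries deleted, one sentence added, one phrase changed) and a note to sites, with no change to design, sample size or analysis.
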